7.1 Selection of Subjects

7.1.1. Subject Population. Subjects will be adults 18 years or older that are already scheduled for a spinal surgery in the neurosurgery or ortho spine clinic.

7.1.2. Source of Research Material.

Source of Research Material	Clinical Purposes (Y/N)	Research Purposes
Oswestry Disability Index	N	Y
Neck Disability Index	N	Y
Pain Catastrophizing Index	N	Y
Fear Avoidance Belief Questionnaire	N	Y

Numeric Pain Rating Scale	N	Y
Healthcare Utilization (MDR Healthcare Database)	Y	Y
The Opioid Risk Tool	N	Y
AHLTA	Y	Y

7.1.3. Inclusion and Exclusion Criteria.

Inclusion criteria (all of the following)

- (a) Any patient currently scheduled for a pre-operative appointment with an orthopaedic spine surgeon or neurosurgeon specifically for a lumbar or cervical procedure.
- (b) Surgery is taking place for a condition that has been ongoing for 6 months or longer (chronic)
- (c) Between the age of 18 - 65 years
- (d) Read and speak English well enough to understand the education, provide informed consent and follow study instructions (the surgeon, associate investigator, or research assistants will make this determination. Any patient that needs an interpreter will not be allowed to enroll).

Exclusion criteria (any of the following)

- (a) Known aversion or allergy that would prevent the patient from taking any opioid-based pain medication

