Pittsburg Sleep Quality Index (PSQI) The Pittsburg Sleep Quality Index (PSQI) is a self-rated questionnaire which assesses sleep quality and disturbances. Clinical properties provide utility in both psychiatric clinical practices and research activities. Seven “component” scores including: subjective sleep quality, sleep latency, sleep duration, habitual sleep efficiency, sleep disturbances, use of sleep medication, and daytime dysfunction are generated from 19 individual items.⁶³ Sleep quality may have a significant role in affecting outcomes of patients with low back pain as several studies have shown correlation between chronic back pain and quality of sleep.^{70, 71}

Fear Avoidance Belief Questionnaire (FABQ): The⁷² will be used to measure patients’ beliefs about how physical activity and work may affect their pain and perceived risk for re-injury. The FABQ contains two subscales; a 7-item work subscale (FABQW), and 4-item physical activity subscale (FABQPA). Test-retest reliability of the FABQ subscales is high,^{72,73} and validity is supported by associations with disability and work loss in patients with acute and chronic LBP.^{74,75} Heightened fear-avoidance beliefs have been shown to be a risk factor for the development of chronic LBP following an acute episode.^{62,76} Other research suggests it may be appropriate for other body regions, specifically evaluating its use in lower extremity injuries within a physical therapy setting.⁷⁷

Healthcare Utilization

Finally, healthcare utilization data will be collected from the MHS Data Repository (MDR) database and will be confirmed via AHLTA. Healthcare utilization data will be used to determine any opioid medication use along with any subsequent medical utilization related to low back or neck pain. In order to collect this information a DUA will be completed between the researcher team and Patient Administration Systems and Biostatistics Activity (PASBA) and the Tricare Management Agency (TMA). Both of these agencies require a signed completed IRB protocol prior to submitting the DUA. However, this should not impact the timing of this study; as the data pull will be completed no sooner than December 2015. This will provide more than enough time to complete the DUA with both agencies and submit the signed DUA to the BAMC IRB prior to performing this analysis. Details for the determining healthcare utilization are outlined below:

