The goal of the MDR database will be to determine the medication utilization for each of these subjects, as well as any other healthcare related to low back pain sought in the 12-month period after treatment in this study. This data (type, location, number of clinic visits, types of specialty clinic visits, imaging, and associated medication) will allow us to determine the extent of low back pain related healthcare utilization for each subject.

- Recording of Extracted Data with Identifiers:

The data will be provided in a de-identified manner from PASBA. As they have done before with members of our team on prior project, they extract all the required data along with name, age and social security number in order to identify the correct subjects that were in our study. They will then assign a pseudo identification number and match that with the list of our subject identification numbers that we provide. Therefore, the final working set they provide us for analysis will not have any identifying PHI/PII associated with it. If additional follow-up is needed to clarify a healthcare utilization event in AHLTA, the research team can check the master subject record (stored on an encrypted government computer) in order to link the subject ID to SSN. Therefore, prior to analysis occurring, the identifiers will be eliminated. Confidentiality of protected health information will be maintained by the research staff at all times, however it should be minimal at this time. The final working database to be used in the data analysis will not include PHI information.

- Location of Extracted and Recorded Data:

The healthcare utilization data will be primarily extracted from the MDR database and through AHLTA. Even though the data is now de-identified, the extracted data will still be maintained in an encrypted, password protected file kept at the Physical Therapy Clinic, Brooke Army Medical Center.

- Nature of Identifying Data

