7.4.1 *Sample Size Estimation.* Collection of healthcare utilization will occur in 100% of the subjects as no follow-up is required, and therefore no opportunities to collect data from a follow-up visit will be lost. Therefore the sample size estimation is based on the secondary outcome variable of self-reported pain and function (OSW). Assuming at least 85% of patients complete the OSW at 6 months, enrollment of 60 subjects per group (total sample size 120 subjects) will provide at least 84% power to detect a difference of 12 points (2 X MCID) on the change in OSW to 26 weeks, assuming a standard deviation in the change in OSW of 16 points (treatment effect = 43.8% of one standard deviation). The MCID for both the OSW and NDI has been estimated at 6 points.⁵⁵ Previous work with patients with acute LBP indicate that these estimates of anticipated effect size and standard deviation are realistic,⁷⁸⁻⁸⁰ and would be consistent with detecting an effect that is at least slightly in excess of the threshold for seeing significant change. The NDI and OSW are similar in length and answer-type, and as we are expecting a higher number of lumbar patients, we will use the OSW to power this study.

Estimate Required Sample Size	101
Estimate Participant Drop Out / Withdrawal	19
Total Enrollment Requirement	120

Enrollment at Each Site	
--------------------------------	--

BAMC	120
------	-----

7.4.2 Primary (i.e., primary outcome variables) and secondary endpoints.

Primary Outcome Variable: Spinal pain healthcare utilization during the 1 year after enrollment understanding patients are likely still receiving care for their surgery at 6 months. This will include a comparison of imaging orders and types, specialty referrals, and medication use (pain and narcotics).

The self-reported outcome measures will also be taken at baseline, 1 month, and 6 months.

7.4.3 Data analysis.

All data will be analysed in IBM SPSS 21 (Chicago, IL). Descriptive statistics will be performed to describe the sociodemographic (age, sex, race, etc.) and health characteristics (disability, pain intensity, psychosocial factors, etc.) of the entire sample, and comparisons made between groups. Means and standard deviations will be computed for continuous data and frequency distributions will be analysed for categorical data.

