Specific Aim #1 will be evaluated by determining the RR (risk ratio) for opioid medication use during the 1 year following surgery between both groups. Utilization reports will be broken down into the 1st week (expected to be the highest), 1st month, and then from 2 through 1 year. We will also look at all healthcare utilization events between patients associated with lumbar ICD-9 codes (Appendix A) in those randomized to also view the educational video.

Comparison of self-report outcomes between groups at baseline and 6 months will be performed using a linear mixed-effects model, which is flexible in accommodating data assumed to be missing at random (Specific Aim #2). The time points will be baseline, 1 month, and 6 months for the measures collected from the patient (self-report questionnaires). Significance is set at 0.05 and 95% confidence intervals will be reported for all relevant data. Sensitivity analysis will be run adjusting for other demographic and/or prognostic variables (PCS, pain intensity, ESS, etc) that may affect the outcome.

Specific Aim #3 will be determined by comparing the variables between each group and introducing them as covariates into the linear mixed-effects model to see if the adjustment influences the differences between each group.

Point estimates with 95% Confidence Intervals will be reported.

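### The analysis section limits utilization events to lumbar codes, although the trial enrols cervical patients and its primary outcome is utilization for spinal pain

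*Combined protocol and SAP*

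**What the plan says.** Three places set a scope that includes the neck:

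- Inclusion criterion (a) in 7.1.3 admits patients scheduled "specifically for a lumbar or cervical procedure".
- Section 7.4.2 names the primary outcome as "Spinal pain healthcare utilization during the 1 year after enrollment", with no limit by region, and adds: "This will include a comparison of imaging orders and types, specialty referrals, and medication use (pain and narcotics").
- The Healthcare Utilization text in 7.3.2 says the data will capture opioid use and "any subsequent medical utilization related to low back or neck pain".

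Two places set a narrower scope:

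- The MDR goal in 7.3.2 asks for each subject's medication use and "any other healthcare related to low back pain sought in the 12-month period after treatment in this study". Its next sentence includes associated medication in the data used to measure low-back-related care.
- Section 7.4.3, after the opioid risk ratio, turns to "all healthcare utilization events between patients associated with lumbar ICD-9 codes (Appendix A"). The sentence then ends by tying this look to the patients assigned to the video.

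The appendix list at the end of the protocol gives Appendix A as the Oswestry form. On the size of the cervical group, 7.4.1 says only that "we are expecting a higher number of lumbar patients".

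**The concern.** Imaging and referrals are two of the three components named for the primary outcome. Take a cervical patient who has a neck MRI and a neck-coded specialty referral in the year after enrolment. An analyst working from 7.4.2 and the opening of 7.3.2 counts both. An analyst working from 7.4.3 counts neither. The plan therefore supports two different event sets for the same outcome, and nothing says which one governs. If that is settled only once the data are in hand, the choice can be made, or appear to have been made, with the results in view.

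Two smaller faults sit in the same sentence of 7.4.3. It does not state a between-arm comparison, since its literal subject is the video group. It also sends the reader to a code list at an appendix letter that belongs to a questionnaire.

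**Working it through.** No stated figure can be recomputed for this point. The plan's only power figure (at least 84%, in 7.4.1) concerns the Oswestry score, not utilization. The check is a comparison of the text.

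| Place | Scope stated | Neck-coded imaging or referral counted? |
|---|---|---|
| 7.1.3 (a) | lumbar or cervical surgery | (eligibility only) |
| 7.4.2 | spinal pain | yes, read with 7.1.3 |
| 7.3.2, opening of Healthcare Utilization | low back or neck | yes |
| 7.3.2, MDR goal | low back, for care beyond medication | no |
| 7.3.2, Redundancy (self-report check) | LBP | no |
| 7.4.3, utilization events | lumbar ICD-9 codes | no |
| 7.4.3, opioid risk ratio | no code limit | not applicable |

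**What each component loses under 7.4.3.**
- Imaging, referrals and visits: neck-coded events are excluded.
- Opioid use: nothing is excluded.
- Other pain medication: unclear. The MDR goal first asks for medication with no region stated, then lists associated medication under low-back care, and 7.4.3 speaks of all utilization events.

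**Size.** The actual loss needs the cervical share and the event rates, and the documents give neither. The following is illustration only. Assume a yes/no event with the same rates in both regions, 60 per arm (7.4.1), and alpha 0.05 (7.4.3) taken as two-sided. Let c be the cervical share and f the fraction of cervical patients' events that also carry a lumbar code. Each observed rate is then the true rate × [1 − c(1 − f)], and

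power = Φ[(d − 1.96·SE0)/SE1], with SE0 = √(2·p̄(1 − p̄)/60) and SE1 = √([p1(1 − p1) + p2(1 − p2)]/60).

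For true rates of 50% vs 25% with full capture: SE0 = 0.0884, SE1 = 0.0854, (0.25 − 0.1732)/0.0854 = 0.90, power 0.82. With c = 0.2 and f = 0 the rates become 40% vs 20%: SE0 = 0.0837, SE1 = 0.0816, (0.20 − 0.1640)/0.0816 = 0.44, power 0.67.

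| Assumed true rates | Full capture | c = 0.2, f = 0 |
|---|---|---|
| 50% vs 25% | 0.82 | 0.67 (40% vs 20%) |
| 30% vs 15% | 0.50 | 0.40 (24% vs 12%) |
| 90% vs 65% | 0.92 | 0.62 (72% vs 52%) |

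For 50% vs 25%, f = 0.5 at c = 0.2 gives 0.75. At c = 0.4 the power is 0.67 (f = 0.5) or 0.50 (f = 0). Power falls in every case, but the drop at c = 0.2 and f = 0 runs from 0.10 to 0.30 depending on rates that are pure assumption. None of these figures estimates the loss in this trial.

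**The case against.** **The sentence in 7.4.3 is only an extra look.** It is worded as an addition to the opioid analysis, so it need not define the primary event set. That reading is fair, and 7.4.2 does call for a comparison of the components without a lumbar limit. 7.4.3 also plans reports by time period without a code limit, although that line follows the opioid risk ratio and may concern opioids only. But no other sentence in 7.4.3 gives a code rule. If this one is set aside, imaging and referrals have none.

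**It is leftover wording and the intent is plain.** Probably so. The page header still says lumbar surgery while the protocol title says spinal, and section 13.0 plans recruitment from the lumbar caseload. Yet the narrow wording sits in the extraction goal and the analysis section, which are the parts an analyst carries out.

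**Stronger readings a reader might infer, which the documents do not support.**
- *The opioid result is compromised.* The opioid risk ratio, which answers Aim 1, carries no code limit.
- *The comparison of arms is biased.* The narrow rule would apply to a randomized comparison, so no systematic bias is expected. Section 7.3 describes no stratification by region, so chance could put more cervical patients in one arm. That is not peculiar to this fault: if event rates differ by region, such an imbalance also affects a spine-wide count.
- *No code list exists.* The appendix list also omits the Neck Disability Index, which the trial uses, so the list looks out of date. It shows a mislabelled reference and no more.
- *A definite amount of power is lost.* The range shown above rules out that claim.

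**Conclusion.** The contradiction stands, and it is in the current text. Sections 7.1.3 and 7.4.2 and the opening of the utilization text in 7.3.2 include cervical patients and neck care; the MDR goal and the code rule in 7.4.3 do not. Followed as written, 7.4.3 removes neck-coded imaging, referrals and visits from the primary outcome and leaves non-opioid pain medication uncertain. The consequences are lost content and precision in those components, and an event set open to choice after the results are seen. The size is unknown and cannot be derived from the documents. The conclusion itself rests only on the wording and on some cervical patients having been enrolled, as the inclusion criterion allows. It should be corrected before the 12-month data are analysed.

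**What to change.** Adopt one scope that matches 7.4.2 and the opening of the utilization text in 7.3.2: lumbar and cervical spine codes for every patient, whichever region was operated on. Then:

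1. In 7.4.3, replace the lumbar code restriction with this scope, and say whether it applies to non-opioid pain medication.
2. In the MDR goal in 7.3.2, replace low back pain with the same scope.
3. State the utilization analysis as video versus usual care.
4. Cite the actual code list in place of Appendix A.
5. If wanted, name codes for the operated region as a sensitivity analysis.
6. Report the LBP-only self-report check as a limitation. It cannot be repeated, because 7.1.6 records that follow-up contact has ended.

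The cost is a few sentences and a wider code list, plus possibly a new extraction. Section 13.0 places a data request in November 2017, and the documents do not say which codes it used. If it used only lumbar codes, the whole window must be pulled again with the wider list, and the agreement under which "a DUA will be completed between the researcher team and Patient Administration Systems and Biostatistics Activity (PASBA") and the other agency must be checked for scope. If it was not limited, only the wording changes. On the section 13.0 timetable, enrolment ends in May 2017, so 12-month follow-up runs to May 2018. A November 2017 request could not hold all of it, and a further request is needed in any case.

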1
2
3
Regional Health Command-Central (RHC-C)
Institutional Review Board

**HUMAN SUBJECTS RESEARCH
PROTOCOL APPLICATION – Part B**

4
5
6
7
CLINICAL TRIALS: NCT02674711
4 May 2018

1
2
1. **PROTOCOL TITLE:** The Effect of a Pain Medication Educational Approach before Spinal Surgery on 6-month Post-Operative Use of Opioid Medication: A Randomized Clinical Trial

1
2
3
4
2. **ABSTRACT**

5
6
7
Background: Opioid-based pain medication use and prescription has increased dramatically in the last two decades, leading to high rates of overdose and utilization for patients with chronic non-cancer pain, despite lack of evidence to support its use. Very little research has looked at educational strategies to help address this problem.

8
9
Design: Randomized clinical trial

0
1
2
3
4
Methods: Subjects will be recruited from the pool of patients coming in for the pre-operative appointment prior to spine surgery. Patients that consent and enroll will be randomized to receive either a brief educational video at this appointment or usual care. Patients will be followed after surgery weekly for the first month, and then again at 6 months to determine their self reported opioid medication utilization patterns. Pain medication prescription and healthcare utilization will also be abstracted from the MDR healthcare database.

5
6
7
Summary: The results from this study will help inform and develop best practice for managing patients taking opioid medication for surgical pain.

8
9
3. **OBJECTIVES/SPECIFIC AIMS/RESEARCH QUESTIONS.**

0
1
2
3
4
This study is a continued project in a line of research aimed at improving the quality of spinal pain management. The purpose of this project is to assess the impact of an educational tool that addresses the latest evidence regarding the use of opioid medication in a patient-centric fashion. We will assess the impact this shared-decision making educational tool has on 12 month health care utilization post operatively and the self reported use of narcotic pain medication usage for the 6 months following lumbar spine surgery.

5
6
7
Specific Aim 1: Evaluate the differences in opioid medication use for the 12-month period after surgery in subjects that received the education prior to surgery compared to those that received usual care education.

8
9
Specific Aim 2: Compare the changes in self-reported outcome measures (pain, disability, and sleep) between groups over the 6-month period after surgery.

0
1
2
3
4

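### The Aim 2 mixed model names no 6-month treatment contrast and does not adjust for the outcome's own baseline; a baseline-adjusted 6-month difference would be more precise at no cost

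*Combined protocol and SAP*

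**What the plan says.** Section 3 sets Aim 2, with a 6-month horizon, as follows: "Compare the changes in self-reported outcome measures (pain, disability, and sleep) between groups". Section 7.4.1 sizes the trial on the same kind of quantity, "to detect a difference of 12 points (2 X MCID) on the change in OSW to 26 weeks". The SD of that change is taken as 16 points.

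The analysis for Aim 2 is in section 7.4.3: "Comparison of self-report outcomes between groups at baseline and 6 months will be performed using a linear mixed-effects model". The next sentence there lists baseline, 1 month and 6 months as the time points for the questionnaires. Baseline is therefore in the model as one of the repeated outcomes.

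Section 7.4.3 does not give the fixed effects, a group-by-time term, the contrast to be reported as the treatment effect, the treatment of baseline, or the covariance structure. Covariates appear only in a sensitivity analysis and under Aim 3. The sensitivity list is open-ended. It names pain intensity and catastrophizing, but not the baseline disability score, which is the baseline of the powered outcome.

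**The concern.** Read literally, the sentence asks for two comparisons, one at each visit. The one at baseline has no inferential purpose: section 7.3 assigns groups at random, so any baseline difference is chance and carries no information about the video.

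That leaves the 6-month result, and the text does not say how it is to be formed. Different estimates fit the wording, with different standard errors, and an analyst could choose among them after seeing the data. The one that makes best use of the measurements already planned, a 6-month difference adjusted for baseline, is not specified. At stake is precision and a fixed target for the outcome on which the sample size rests. No bias or inflated error rate follows from the model itself.

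**Working it through.** **Inputs.** From section 7.4.1: difference 12 points; SD of change 16; 60 per group with 85% completing, so 60 × 0.85 = 51 per arm. From section 7.4.3: alpha 0.05, taken as two-sided because no side is stated. The documents do not give the correlation ρ between baseline and 6-month scores, so 0.3, 0.5 and 0.7 are assumed. Also assumed: the same SD and the same correlation across the three visits, and complete data on 51 per arm. Power is from the noncentral t distribution.

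**The plan's own figure.** The standard error of the difference in change is 16 × √(2/51) = 3.17.
- For 12 points (12/16 = 75% of an SD), power is 96.3%.
- Section 7.4.1 also prints "treatment effect = 43.8% of one standard deviation". That is 0.438 × 16 = 7 points, for which power is 59.0%.

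Neither gives the printed 84%. "will provide at least 84% power" is true as a floor for 12 points and false for 7. This conflict is a separate problem, so both effects are carried below.

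**Candidate 6-month estimates.** The SD at one visit is S = 16/√(2(1−ρ)), which gives 13.52, 16.00 and 20.66.
- Difference in change (group-by-time contrast, arm means free at every visit): generalized least squares on three visits gives a standard error of 3.17, the same as the simple change-score comparison.
- Unadjusted 6-month difference: S × √(2/51).
- Baseline-adjusted 6-month difference: S × √(1−ρ²) × √(2/51). Constraining the arm means to be equal at baseline gives the same standard error.

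| | ρ = 0.3 | ρ = 0.5 | ρ = 0.7 |
|---|---|---|---|
| SE, change | 3.17 | 3.17 | 3.17 |
| SE, unadjusted 6-month | 2.68 | 3.17 | 4.09 |
| SE, baseline-adjusted | 2.56 | 2.74 | 2.92 |
| Variance, adjusted ÷ change = (1+ρ)/2 | 0.65 | 0.75 | 0.85 |
| Variance, adjusted ÷ unadjusted = 1−ρ² | 0.91 | 0.75 | 0.51 |
| Power at 12 points: change | 96.3% | 96.3% | 96.3% |
| Power at 12 points: unadjusted 6-month | 99.3% | 96.3% | 82.8% |
| Power at 12 points: adjusted | 99.6% | 99.1% | 98.2% |
| Power at 7 points: change | 59% | 59% | 59% |
| Power at 7 points: adjusted | 77% | 71% | 66% |

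The adjusted estimate has the smallest standard error in every column. Change and the unadjusted 6-month score change places at ρ = 0.5: below it the 6-month score alone is more precise, above it change is.

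If a single group effect averaged over the three visits were reported, it would include baseline, where no effect can exist. A true effect δ that is equal at 1 and 6 months would then appear as (0 + δ + δ)/3, two-thirds of its size.

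**The case against.** The sentence can be read more kindly. It serves an aim that is about change, and it is followed by a list of time points that includes baseline. The ordinary reading is then a repeated-measures model whose group-by-time contrast is the difference in change, which is what section 7.4.1 powered. That contrast is valid under randomization. At the stated 12 points it already has about 96% power, so adjustment adds only 2 to 3 percentage points. The larger gain at 7 points comes with a low starting power that belongs to the effect-size conflict in section 7.4.1, not to the handling of baseline. The outcome is also secondary: section 7.4.2 makes healthcare utilization primary.

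Most of this stands, and it rules out two stronger readings. A reader might infer that the analysis targets a different quantity from the one powered. The documents do not show that: the model as described can deliver exactly the powered contrast, with the same standard error of 3.17. The contrast is unnamed, not shown to be different. A reader might also infer that the baseline measurement is thrown away. That would be so only if the unadjusted 6-month difference were the reported result, and the plan does not say it will be.

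Timing is a fair point too. Section 7.1.6 says follow-up was complete at the April 2018 amendment, and section 13.0 schedules the analysis to finish in May 2018. A change at that stage has to be dated and justified. None of this answers the point that the contrast is unnamed and that a more precise estimate is available from the same data.

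**Conclusion.** The point holds as a gap in specification with a free gain in precision. The Aim 2 model does not name its 6-month treatment contrast, does not adjust for the outcome's own baseline, and includes a baseline comparison that cannot inform the treatment effect.

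Against the difference in change, adjustment lowers the variance by 35%, 25% and 15% at ρ = 0.3, 0.5 and 0.7. Against the unadjusted 6-month difference, it lowers it by 9%, 25% and 49%. In power this is small at 12 points and material at 7 points, and the plan must settle which effect it means.

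The percentages rest on the assumed correlations and on equal SDs at the two visits; they do not depend on the sample size. The power figures also follow section 7.4.1 in letting all 51 per arm contribute to the Oswestry analysis, although section 7.3 gives that form only to lumbar patients. Importance is moderate: the outcome is secondary, but the sample size was set on it.

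**What to change.** Rewrite the Aim 2 paragraph of section 7.4.3 to do the following:
- Name the arm difference at 6 months, with its 95% confidence interval, as the Aim 2 estimate for each self-report outcome.
- Fit a mixed model with 1 and 6 months as outcomes, the outcome's own baseline value as a covariate, and arm, visit and arm-by-visit as fixed effects. Alternatively, keep all three visits as outcomes and constrain the arm means to be equal at baseline.
- Use an unstructured covariance matrix across visits.
- Remove the between-group comparison at baseline and keep baseline values as description only.

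Under randomization this estimates the same treatment effect as the difference in change, so the sample size is not threatened: power is higher than for change in every case examined. It needs no new patients, data or software, only wording. Because follow-up was already complete by April 2018, the change should be dated, justified, and made before any between-group analysis. If such an analysis has already been run, report the difference in change beside the adjusted estimate and say which was chosen first.

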Specific Aim 3: Describe the sociodemographic factors and healthcare utilization in enrolled subjects for the 12 months leading up to a surgical procedure for the lumbar spine. Identify factors that could account for differences in opioid medication, and any potential interaction effect between intervention, opioid use, and clinical outcomes following surgery.

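### The Aim 2 main model fixes no prognostic covariates, and Aim 3 draws its covariates from between-arm comparisons, which leaves precision unused and the main estimate unstated

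*Combined protocol and SAP*

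**What the plan says.** Section 7.4.3 holds the whole analysis plan for the self-report outcomes.

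- **Baseline description.** Sociodemographic and health characteristics are summarised "of the entire sample, and comparisons made between groups". No test is named.
- **Aim 2.** "Comparison of self-report outcomes between groups at baseline and 6 months will be performed using a linear mixed-effects model". Baseline, 1 month and 6 months are the time points. No covariate is named.
- **Aim 2, adjusted version.** "Sensitivity analysis will be run adjusting for other demographic and/or prognostic variables (PCS, pain intensity, ESS, etc) that may affect the outcome".
- **Aim 3.** The method is "comparing the variables between each group and introducing them as covariates into the linear mixed-effects model". The adjusted fit is then judged by whether it shifts the arm difference. There is no final list, no selection threshold, and no definition of when an adjustment counts as having an influence.

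Section 3 states the purpose of Aim 3 more broadly: "Identify factors that could account for differences in opioid medication, and any potential interaction effect between intervention, opioid use, and clinical outcomes following surgery". Section 7.4.2 places the primary outcome elsewhere: "Primary Outcome Variable: Spinal pain healthcare utilization during the 1 year after enrollment". Opioid use under Aim 1 is compared by a risk ratio, outside the mixed model.

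**The concern.** Two features of this plan are weak for a randomized comparison.

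The first is the route to the covariates. After proper randomization, a between-arm difference in a baseline variable reflects chance. It says nothing about whether the variable predicts the outcome, and prediction is what makes adjustment worthwhile. Whether the treatment estimate moves is likewise a poor way to judge an adjustment.

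The second is that nothing is fixed in advance. The Aim 2 list is open-ended. It includes ESS, which is undefined and appears in neither the source table (7.1.2) nor the assessment schedule (7.3). It also includes PCS and pain intensity, which the schedule places at 1 and 6 months as well as at baseline; the text does not restrict the adjustment to baseline values. Section 5 itself describes pre-operative opioid use as a predictor of worse outcome after spine surgery, and the prior 12 months of MDR data are to be collected, yet no model names that variable. Surgical region is in no model either, and section 7.3 names no stratification factor.

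At stake are the width of the intervals for the self-report outcomes and a clear statement, made in advance, of which estimate carries the Aim 2 conclusion.

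**Working it through.** **Step 1. The plan's own power figure.** Section 7.4.1 gives 60 per arm, 85% completing (60 × 0.85 = 51 per arm), an SD of change of 16, a difference of 12 points, an effect of 43.8% of an SD, and at least 84% power. Section 7.4.3 gives the level: "Significance is set at 0.05 and 95% confidence intervals will be reported for all relevant data". It does not state sidedness, so I take two-sided.

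- SE = 16 × √(2/51) = 3.168
- Power = Φ(δ/SE − 1.96)
- δ = 12: Φ(3.788 − 1.96) = 96.6%
- δ = 0.438 × 16 = 7.008: Φ(2.212 − 1.96) = 60%

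Neither gives 84%, which corresponds to about (1.96 + 0.994) × 3.168 = 9.4 points. At least 84% is literally met at 12 points but not at 43.8% of an SD, and 12/16 is 75%, not 43.8%. That inconsistency is a separate matter. Because both effects are stated, I carry both forward.

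**Step 2. Fixed adjustment.** If baseline covariates explain a share R² of the variance of the change, the residual SD is 16 × √(1 − R²). For R² = 0.25 this is 13.86, so SE = 13.86 × √(2/51) = 2.744 and the half-width is 1.96 × 2.744 = 5.4. The documents give no R², so a range is shown.

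| R² (assumed) | SE | 95% CI half-width | Power, 7.0 points | Power, 12 points |
|---|---|---|---|---|
| 0 (unadjusted) | 3.168 | 6.2 | 60% | 96.6% |
| 0.09 | 3.023 | 5.9 | 64% | 97.8% |
| 0.25 | 2.744 | 5.4 | 72% | 99.2% |
| 0.36 | 2.535 | 5.0 | 79% | 99.7% |
| 0.49 | 2.263 | 4.4 | 87% | 99.96% |

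This formula ignores the small cost of estimating the covariate coefficients. Step 3 includes it.

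**Step 3. How the covariates are chosen.** The simulation used 8,000 trials per setting, 51 per arm, and 3 or 6 independent, equally prognostic covariates. The selection rules are assumptions; the plan states none.

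| Analysis | Power at 7.0 points, R² 0.25 | Power at 7.0 points, R² 0.5 | Rejection under no effect |
|---|---|---|---|
| Unadjusted | 59% | 58–61% | 4.4–5.1% |
| Fixed covariates | 68–70% | 86% | 4.5–5.0% |
| Only covariates with baseline p < 0.05 | 59–60% | 60–62% | 3.6–4.4% |
| Adjust only if the estimate moves by more than 10% | 66–68% | 81–82% | 3.7–4.3% |
| Report the smaller p-value of unadjusted and adjusted | 73–74% | 87–88% | 6.7–8.2% |

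Selection by imbalance gives up almost all of the gain. The unadjusted and fully adjusted tests disagree on significance in 18–31% of trials at 7.0 points, and in about 3–4% at 12 points.

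**Step 4. Chance imbalance.** With 5 independent baseline comparisons the probability of at least one p < 0.05 is 1 − 0.95⁵ = 23%; with 10 it is 1 − 0.95¹⁰ = 40%.

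**The case against.** The case on the other side is substantial and narrows the point in several places.

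- **Only imbalanced variables enter.** A reader might infer this from the Aim 3 sentence. The text does not say it: the compared variables are introduced, with no threshold. If all of them enter, the Aim 3 model keeps its precision. The near-total loss in Step 3 applies only if the wording is read as selection by imbalance. What remains on either reading is that the Aim 2 model has no named covariates and so forgoes the gain in Step 2.
- **Two rival treatment estimates.** A reader might infer this too. Section 7.4.3 calls the Aim 2 adjustments a sensitivity analysis and describes them partly as prognostic, which implies that the unadjusted model leads. That stands, but it is never stated outright, and the label is not attached to the Aim 3 models.
- **Inflated type I error.** The 7–8% arises only if the analyst reports the more favourable estimate. The plan does not call for that, though it does not exclude it. Selection by imbalance alone is conservative.
- **Scope.** Aim 3 is framed as descriptive and explanatory, and the primary utilization outcome is not analysed with this model. Both are correct. The affected outcomes are secondary, but section 7.4.1 sizes the trial on one of them.
- **Baseline is already a time point.** Some of the precision from the baseline value may therefore be recovered. That does not extend to opioid history, risk score or region.
- **An unadjusted main model is valid.** This is true. The case for changing it rests on efficiency and clarity, not on bias.

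**Conclusion.** The point holds as a weakness of efficiency and specification in the secondary self-report analyses. Between-arm comparison is a poor way to arrive at covariates, no covariate set is fixed, and the main estimate is only implied.

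The size depends on quantities that the documents do not give. At an assumed R² of 0.25, the half-width falls by 0.8 points and power at 7.0 points rises by about 12 percentage points by formula, or about 9 to 11 in the simulation. At an R² of 0.09 the gain is about 4 points. At a true difference of 12 points there is almost no power to gain, though the interval still narrows. These figures treat the 6-month change as a single comparison and, as section 7.4.1 does, count all 51 completers per arm on the OSW, although cervical patients complete the NDI. Any precision that the mixed model already recovers from baseline would reduce the gain.

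The documents do not support a claim that the plan is bound to lose precision through selection by imbalance, that it inflates type I error as written, or that the primary outcome is compromised.

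**What to change.** Amend section 7.4.3 as follows.

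1. For Aim 2, name the adjusted mixed model as the main analysis and the unadjusted one as supportive.
2. Fix a short list of pre-randomization covariates chosen for prognostic value: the baseline value of the outcome, pre-operative opioid use from the MDR, the Opioid Risk Tool score, and surgical region where lumbar and cervical patients are analysed together. Within the OSW or NDI alone, region is constant and drops out.
3. Handle the baseline value in one way only: as a covariate for the 1- and 6-month outcomes, or by keeping baseline among the outcomes with the arm means constrained to be equal.
4. State that all adjustment variables are baseline values, and remove ESS.
5. Describe baseline characteristics by arm, but do not use between-arm comparisons to choose covariates. Label the Aim 3 adjustments exploratory.

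The cost is a few sentences; the schedule in section 7.3 already collects every variable needed. The small downside is timing. Section 7.1.6 records that participant follow-up was complete at the April 2018 amendment, so the list must be dated and fixed before any by-arm analysis. If that is no longer possible, the report must say so.
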